8.5.2 Discontinuation of treatment WITHOUT progressive disease

If a patient discontinues treatment **without** progressive disease (clinical progression or radiologically assessed progression), he/she will be followed every 8 weeks (+/- 2 weeks) until progression of disease.

- AE/SAE assessment, per Section 8.5.1, must be done at the first follow-up visit after discontinuation at the latest.
- Research blood will be drawn at the time of disease progression.
- If a patient discontinues treatment without progressive disease and a new line of antineoplastic therapy is initiated, he/she will be censored for progression at that time point, research blood should be drawn, and AE/SAE follow up will cease.
- Upon disease progression or censoring for progression, the patient will be followed for survival per the progressive disease follow-up schedule in Section 8.5.3.

Follow-up will include collection of data of the following procedures. The procedures are not required every 8 weeks, but information from such procedures that are done per standard of care procedures will be collected if performed:

- Physical examination, including vital signs, weight and ECOG performance status
- Complete blood count, including platelets and differential
- Blood chemistries:
 - o BUN, creatinine, electrolytes (K+, Na+, Cl-, CO2), glucose, calcium, magnesium
- Liver function tests:
 - Total protein, albumin, total bilirubin, AST (SGOT), ALT (SGPT), and alkaline phosphatase

- Adverse event follow-up per Section 8.5.1.
- Survival Assessment
- Research blood for correlative studies at the time of disease progression as noted above.
- Tumor measurements according to RECIST 1.1

8.5.3 Progressive disease follow-up

Patients who discontinue treatment with progressive disease, experience progression during non-progressive disease follow up, or are censored for progression, will be followed for survival every 12 weeks (+/- 2 weeks) for 2 years.

AE/SAE assessment will be performed by phone contact or per a standard of care visit at least 60 days after the last dose of study drug, and per the requirements in Section 8.5.1.

9. BIOMARKER, CORRELATIVE, OR SPECIAL STUDIES

Any remaining biospecimens collected for the research will be placed in a biorepository if subjects agree and consent to future use of their samples.

9.1 Submission of archived diagnostic tissue

For randomized subjects, submission of primary tumor tissue blocks (or slides, if blocks are not available) from procedures **prior to clinical cetuximab exposure** should be submitted for biomarker correlatives. This includes: A representative paraffin block of the original diagnosis and/or any repeat diagnostic biopsies, if available. Include a copy of the corresponding pathology report with the archived tissue. Collection, preparation, and shipping information for the archived tissue is in the Lab Manual. All efforts must be made to obtain paraffin blocks. If paraffin blocks are not available or the pathology department will only release slides, please contact the Sponsor-Investigator prior to requesting slides. A 3 mm core, punched from the tissue block with a punch tool, and 5-10 unstained slides of 5 micron thickness mounted on positively-charged glass slides may be acceptable.

9.2 Research biopsy

All patients will be evaluated for a research biopsy at the time of enrollment. The biopsy is to be done prior to initiation of protocol treatment. Biopsies of primary tumor, accessible metastatic tumor, cutaneous lesion, or lymph node can occur in the outpatient office of the head and neck surgeon, with local anesthetic per standard of care. Biopsies of lymph nodes requiring imaging

guidance or distant metastases will occur under the care of an interventional radiologist, with ultrasound or CT guidance and local anesthetic per standard of care.

Omission of the research biopsy is allowed if performing the biopsy is not safe and/or feasible, and/or would present unacceptable clinical risk. Contact the Sponsor-Investigator for approval to omit the research biopsy. If the research biopsy is omitted, archived tumor tissue should be collected to substitute for the lack of baseline tissue. The archived tissue substituted for the Research Biopsy should be the **most recent** biopsy available and the corresponding pathology report must be obtained. (Substitution of archived tumor tissue for the research biopsy is independent of the archived tissue submission described above in Section 9.1.)

9.2.1 Research Biopsy Methodology

Research biopsies will consist of a cup forceps biopsy, a core needle biopsy, or a punch biopsy that can be safely performed in the outpatient setting with only local anesthesia. During the biopsy procedure, at least two cores of tissue 1-cm in length should be obtained with an 18-guage core biopsy needle (18-gauge or greater is preferred; 20-gauge is acceptable) – or the equivalent with cup forceps biopsy.

Collection, preparation, and shipping information for the research biopsy is in the Lab Manual.

9.3 Research Blood

Blood for research purposes will be collected at the following time points:

- baseline
- end of cycles when a tumor assessment is due (Refer to Section 8.3.2 and Section 8.3.3)
- at the end of treatment if not collected within the prior 14 days
- at disease progression if not collected within the prior 14 days

Peripheral blood obtained by venipuncture will serve as the source for laboratory testing. Up to 70 mL of blood may be obtained at each draw. See the Lab Manual for collection information. Research blood will be used for correlative research and will be batch processed.

10.STATISTICAL METHODS

10.1 Study Design

This is an open-label phase II trial with a randomized, non-comparative, two-arm design (Arm A: ficlatuzumab vs. Arm B: ficlatuzumab + cetuximab) in patients with recurrent and/or metastatic head and neck squamous cell carcinoma after failure of anti-EGFR therapy.

10.2 Primary Objective

The primary objective is to estimate the efficacy of ficlatuzumab, with or without cetuximab, as measured by the endpoint of PFS. Patients will be evaluable for PFS from the time of their first treatment with ficlatuzumab. PFS will be measured from the date of randomization until the date of progression or death. Patients without progression will be censored at the date of last follow up.

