3.2 Exclusion Criteria

Patients meeting any of the following exclusion criteria are not to be enrolled in the study:

- Nasopharyngeal primary site if WHO Type III (non-keratinizing and EBV-positive as established at the local site).
- History of severe allergic or anaphylactic reactions or hypersensitivity to recombinant proteins or excipients in the investigational agent.
- Prior treatment with an HGF/cMet inhibitor such as rilotumumab, crizotinib, MetMAb, or ARQ197.
- Uncontrolled central nervous system (CNS) metastases, including leptomeningeal metastases, are not allowed.

Note: Subjects with previously treated brain metastases will be allowed if the brain metastases have been stable without steroid treatment for at least 2 weeks (radiotherapy or surgery).

- Failure to recover to Grade 1 or baseline from all toxic effects of previous chemotherapy, radiation therapy, biologic therapy, immunotherapy, and/or experimental therapy, with the exception of:
 - Alopecia,
 - Grade ≤ 2 peripheral neuropathy,
 - Grade ≤ 2 cetuximab-related rash or other skin changes,
 - o Hypomagnesemia (acceptable values detailed in the exclusion criteria below),
 - o Hypokalemia (acceptable values detailed in the exclusion criteria below), and

- The acceptable ANC and PLT inclusion criteria values above.
- Treatment with cetuximab 2 weeks prior to the first dose of study drug. A washout period of 2 weeks from prior cetuximab is required if applicable.
- Treatment with cytotoxic chemotherapy, targeted therapy, immunotherapy or investigational drug 3 weeks prior to the first dose of study drug. A washout period of 3 weeks from any prior cytotoxic chemotherapy, targeted therapy, immunotherapy or investigational drug is required, if applicable.
- Significant underlying pulmonary disease, including pulmonary hypertension or interstitial pneumonitis.
- Peripheral edema ≥ Grade 2 per NCI-CTCAE version 4.0.
- Significant cardiovascular disease, including:
 - o Cardiac failure New York Heart Association (NYHA) class III or IV.
 - Myocardial infarction within 6 months prior to registration.
 - Severe or unstable angina within 6 months prior to registration.
 - History of serious ventricular arrhythmia (i.e., ventricular tachycardia or ventricular fibrillation).

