| Any | PD*** | Yes or No | PD | No prior SD, PR or CR |
| Any | Any | Yes | PD | |

^{*} See RECIST 1.1 manuscript for further details on what is evidence of a new lesion.

Note: Patients with a global deterioration of health status requiring discontinuation of treatment without objective evidence of disease progression at that time should be reported as "symptomatic

^{**} Only for non-randomized trials with response as primary endpoint.

^{***} In exceptional circumstances, unequivocal progression in non-target lesions may be accepted as disease progression.

deterioration." Every effort should be made to document the objective progression even after discontinuation of treatment.

CR = complete response; PR = partial response; SD = stable disease; PD = progressive disease

First Documentation of Response

The time between initiation of therapy and first documentation of PR or CR.

Confirmation of Response

To be assigned a status of complete or partial response, changes in tumor measurements must be confirmed by repeat assessments performed no less than four weeks after the criteria for response are first met.

Duration of Response

Duration of overall response - the period measured from the time that measurement criteria are met for complete or partial response (whichever status is recorded first) until the first date that recurrent or progressive disease is objectively documented, taking as reference the smallest measurements recorded since treatment started.

Duration of Overall Complete Response

The period measured from the time measurement criteria are met for complete response until the first date that recurrent disease is objectively documented.

Duration of Stable Disease

A measurement from registration until the criteria for disease progression is met, taking as reference the smallest measurements recorded since registration. To be assigned a status of stable disease, measurements must have met the stable disease criteria at least once after study entry at a minimum interval of eight weeks (+/- 1 week).

Survival

Survival will be measured from the date of entry on study.

Time to Progression and Progression-free survival

This interval will be measured from the date of entry on the study to the appearance of new metastatic lesions or objective tumor progression.

Progression-free survival (PFS) will be calculated from treatment initiation to disease progression or death from any cause.

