10.3 Sample Size Determination

The primary objective of this study is to estimate PFS in both arms. The sample size calculation thus is based on the primary endpoint of PFS. Given no data are available for single-agent ficlatuzumab in patients with recurrent and/or metastatic HNSCC refractory to platinum, cetuximab, and PD-1 inhibition, the historical control will be represented by dealer's choice chemotherapy in the phase III trial of nivolumab in platinum-refractory HNSCC: 2 months. This median PFS is very similar to single-agent data in the refractory, recurrent and/or metastatic setting for cetuximab, afatinib, and methotrexate ^{49, 50}. We would like to investigate whether the new regimen in either arm can improve the median PFS from 2 months to 3.33 months (i.e. 60% improvement in median PFS). To detect such an improvement, the study design requires 66 eligible patients (33 eligible patients on each arm) over 24 months with an additional follow-up of 6 months (making the study duration of approximately 2.5 years in total), using a log-rank test with 90% power while assuming a 0.10 one-sided type 1 error rate. Full information for the primary endpoint of PFS will occur at 33 events per arm. To account for an assumed 10% ineligibility/drop-out rate, 74 patients in total will be accrued to obtain the necessary 66 eligible randomized patients. If one arm achieves the hypothesized median PFS, that arm will be advanced to phase III testing. If both arms achieve the hypothesized PFS, the numerically superior arm will be advanced to phase III testing.

Definition of Evaluable:

Subjects who receive at least one dose of ficlatuzumab will be considered evaluable.

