10.4.2 Other Efficacy Endpoints

Response rate will be assessed by modified RECIST criteria, version 1.1. Overall survival will be measured from the date of randomization until the date of death.

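### Primary PFS has two conflicting start dates, and Section 10 counts from randomization in a set restricted to patients who lived to receive ficlatuzumab

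*Combined protocol and SAP*

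**What the plan says.** **Start of the primary endpoint.** Section 10.2: "PFS will be measured from the date of randomization until the date of progression or death". Section 6.2, under the heading for time to progression and PFS: "Progression-free survival (PFS) will be calculated from treatment initiation to disease progression or death from any cause". Nothing ranks one above the other. Section 10.6 names Kaplan-Meier estimation but gives no origin and no analysis set.

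**A third phrase.** Just before the Section 6.2 definition comes: "This interval will be measured from the date of entry on the study to the appearance of new metastatic lesions or objective tumor progression". It omits death, so it is probably the time-to-progression definition, although it is not labelled as such. Entry is undefined but probably means randomization: Section 6.2 has "Survival will be measured from the date of entry on study" and Section 10.4.2 has "Overall survival will be measured from the date of randomization until the date of death". I do not count it as another PFS origin.

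**Who is analysed.** Section 10.2: "Patients will be evaluable for PFS from the time of their first treatment with ficlatuzumab". Section 10.3: "Subjects who receive at least one dose of ficlatuzumab will be considered evaluable".

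**What governs the gap.** Section 8.2 has the assignment typically returned the same or next day. Section 3.2 counts washout back from first dose, excluding "Treatment with cytotoxic chemotherapy, targeted therapy, immunotherapy or investigational drug 3 weeks prior to the first dose of study drug"; the 2-week cetuximab washout is anchored the same way. I found no maximum interval from randomization to first dose.

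**Futility.** Section 10.7 uses progression-free status at 16 weeks and does not say from when.

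**The concern.** There are two separate faults.

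1. The same patient has two PFS times that differ by the whole randomization-to-dose gap. Two analysts following the document could report different medians from the same data.
2. Even if Section 6.2 is set aside, Section 10 is inconsistent with itself. Its clock starts at randomization, but a patient enters the set only on receiving ficlatuzumab. Those who die first are dropped, and those who remain could not have died in the gap. This is guaranteed (immortal) time. Compared with a clock and set that agree, it can only lengthen PFS.

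In a trial comparing its arms, similar gaps would largely cancel. This one is non-comparative (Section 10.1), and each arm is set against a 2-month historical median (Section 10.3). An arm that reaches the hypothesized 3.33 months goes to phase III. If both do, the numerically better one goes, so a gap that differed by arm could also affect that choice.

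**Working it through.** **The plan's own figures first.** Sixteen weeks is 112/30.4375 = 3.68 months. With exponential PFS, the null progression-free rate is exp(−ln2 × 3.68/2) = 0.279. Running the Section 10.7 boundaries exactly at 0.279 gives a 0.097 chance that a null arm passes, early termination 0.86 and expected size 21.2. At 0.46 it gives power 0.80 and expected size 31.4. The plan states α = 0.10, 0.86, 21.3, 80% and 31.4, so the rule reproduces. The accrual figure also reproduces: 66/0.9 = 73.3, rounded up to 74.

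**Inputs.** 33 patients per arm, 33 events, null median 2 months, target 3.33 months and one-sided 0.10 (Section 10.3). Median survival is 6 months (Section 1.1 says less than 6), varied from 5 (assumed) to 8.2 months (the phase Ib figure, Section 1.4). Gaps of 3, 7, 14 and 21 days are **assumptions**, equal for all patients; 21 days is the longest washout.

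**One patient.** Progression at the first scheduled scan, 56 days after first dose, is 56/30.4375 = 1.84 months on the Section 6.2 clock. On the Section 10.2 clock it is 1.94, 2.07 and 2.30 months at gaps of 3, 7 and 14 days.

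**One arm.** The one-sample log-rank statistic is Z = (E − O)/√E with O = 33. Z > 1.2816 requires E > 41.23. With hazard λ = ln2/2 = 0.3466 and no gap, E is Gamma(33), and P(E > 41.23) = 0.083. Two models bracket a gap of g months:

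- *Deaths only.* The death hazard is δ = ln2/OS, progression makes up the rest of λ, and patients who die in the gap are replaced. PFS among those kept is exp(−λt)/exp(−δg) for t > g, so the null median is 2 + (2/OS)g. Type I error is by simulation (300,000 arms).
- *All events.* Any PFS event before dosing removes the patient, so PFS is the gap plus an exponential time. The null median is 2 + g, and type I error is P(Gamma(33) > 41.23 − 33λg).

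The median rule is the chance that at least 17 of 33 times exceed 3.33 months. The futility rows apply only if the 16-week clock starts at randomization.

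| Gap (days) | 0 | 3 | 7 | 14 | 21 |
|---|---|---|---|---|---|
| Pre-dose deaths, OS 6 (%) | 0 | 1.1 | 2.6 | 5.2 | 7.7 |
| Null median, deaths only, OS 6 | 2.00 | 2.03 | 2.08 | 2.15 | 2.23 |
| Type I, deaths only, OS 6 | 0.083 | 0.091 | 0.104 | 0.130 | 0.157 |
| Type I, deaths only, OS 8.2 to 5 | 0.083 | 0.090–0.093 | 0.099–0.110 | 0.115–0.141 | 0.134–0.177 |
| Type I, all events | 0.083 | 0.112 | 0.163 | 0.288 | 0.454 |
| Null arm, observed median ≥ 3.33, deaths only, OS 6 | 0.013 | 0.015 | 0.018 | 0.023 | 0.030 |
| Same, all events | 0.013 | 0.019 | 0.030 | 0.063 | 0.122 |
| Null arm passes futility, deaths only, OS 6 | 0.097 | 0.105 | 0.116 | 0.136 | 0.160 |
| Same, all events | 0.097 | 0.121 | 0.160 | 0.248 | 0.362 |

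If the futility status is read at the Cycle 4 scan, its clock runs from first dose and the pass rate stays at 0.097.

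**The case against.** The strongest reply is that the gap is probably short. The assignment comes back within a day or so, and Section 8.1 wants baseline work close to the start of treatment. At 1 to 2 days, type I error is 0.087–0.089 (deaths only) or 0.092–0.102 (all events). A washout-driven 21-day gap would need registration on the day of the last prior dose, and Section 3.2 also requires recovery from earlier toxicity. Nor would every patient wait: with one third delayed, the deaths-only figure is 0.096 at 14 days and 0.104 at 21. A constant death hazard may also overstate early deaths in ECOG 0–1 patients. All this stands, and the 14- and 21-day columns are stress cases.

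The choice of test is partly mine. Section 10.3 says log-rank without saying one-sample, and Section 10.6 plans only Kaplan-Meier curves. On the literal 3.33-month rule, the deaths-only change is small in absolute terms.

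The single-patient example shows only that the clocks differ. The ±7-day scan window alone spans 49 to 63 days, or 1.61 to 2.07 months.

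The documents do not give the origin used for the historical 2 months. If it was randomization, the Section 10.2 clock matches it and only the loss of pre-dose events biases the result. The all-events row would then need its own justification, and a first-dose clock could itself mismatch the benchmark.

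Finally, keeping randomization and widening the set is equally coherent. I accept that.

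These points limit the size of the bias. None reconciles the two definitions or matches the Section 10 clock to its set.

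**Conclusion.** The concern holds. Current text gives two start dates for the primary endpoint. The statistical section joins a randomization clock to a ficlatuzumab-dosed set, which guarantees survival up to first dose. What is guaranteed is survival, not freedom from progression. With the first on-study scan at about 8 weeks, however, progression in the gap would seldom be dated there.

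The direction is known: longer PFS than an analysis whose clock and set agree, and no concurrent control to absorb it. The size is not known, because the gap is undocumented. Up to about a week, the deaths-only model leaves type I error near its nominal 0.10. At 14 days the range is 0.115 to 0.288 across both models and the survival values tried. These figures assume exponential PFS, all 33 events observed, equal gaps and a one-sample log-rank test. The futility effect is conditional on a clock that Section 10.7 does not state. This should be corrected, but it does not by itself invalidate the design.

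**What to change.** - **One definition.** Put a single PFS definition (progression or death from any cause) in Sections 6.2 and 10.2, with an origin that matches its set. The simplest is first dose with the ficlatuzumab-dosed set, as Section 6.2 already has it. Randomization with all eligible randomized patients is an acceptable alternative.
- **Futility.** State the same origin for the 16-week status in Section 10.7. With first dose, it coincides with the Cycle 4 scan.
- **Sensitivity analysis.** If first dose is chosen, also report PFS from randomization in all eligible randomized patients, as far as data exist.
- **Reporting.** Give the randomization-to-first-dose interval and the number never dosed, by arm.
- **Wording.** Label which Section 6.2 sentence defines time to progression, and define study entry. If PFS moves to first dose while survival stays at randomization, say so wherever the two are shown together.

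**Cost.** Text edits and one extra analysis. The primary change needs only randomization and first-dose dates. The sensitivity analysis may be incomplete: Sections 5.4 and 8.5 describe follow-up for patients who stop treatment, so progression data on never-dosed patients may not exist. Observed PFS becomes shorter by each patient's gap relative to Section 10.2, so the correction works against the drug. Dosing ended by March 31, 2021 (Section 5.1) and this version is dated 05/23/2023, so the change must be recorded as made after dosing ended.

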10.3 Sample Size Determination

The primary objective of this study is to estimate PFS in both arms. The sample size calculation thus is based on the primary endpoint of PFS. Given no data are available for single-agent ficlatuzumab in patients with recurrent and/or metastatic HNSCC refractory to platinum, cetuximab, and PD-1 inhibition, the historical control will be represented by dealer's choice chemotherapy in the phase III trial of nivolumab in platinum-refractory HNSCC: 2 months. This median PFS is very similar to single-agent data in the refractory, recurrent and/or metastatic setting for cetuximab, afatinib, and methotrexate ^{49, 50}. We would like to investigate whether the new regimen in either arm can improve the median PFS from 2 months to 3.33 months (i.e. 60% improvement in median PFS). To detect such an improvement, the study design requires 66 eligible patients (33 eligible patients on each arm) over 24 months with an additional follow-up of 6 months (making the study duration of approximately 2.5 years in total), using a log-rank test with 90% power while assuming a 0.10 one-sided type 1 error rate. Full information for the primary endpoint of PFS will occur at 33 events per arm. To account for an assumed 10% ineligibility/drop-out rate, 74 patients in total will be accrued to obtain the necessary 66 eligible randomized patients. If one arm achieves the hypothesized median PFS, that arm will be advanced to phase III testing. If both arms achieve the hypothesized PFS, the numerically superior arm will be advanced to phase III testing.

Definition of Evaluable:

Subjects who receive at least one dose of ficlatuzumab will be considered evaluable.

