10.6 Statistical Analysis Plan

Progression-free and overall survival will be estimated for each arm using a Kaplan-Meier curve. Toxicities and the response rate will be tabulated and reported with 95% exact confidence intervals. The relationship between progression-free survival and the candidate biomarkers will be assessed using Cox proportional hazards models. The relationship with clinical response will be assessed using logistic regression models.

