10.7 Continuous Monitoring Rule for Futility

The study will include a continuous Bayesian monitoring rule for futility. We will accrue and observe the first 8 evaluable patients on each arm, then continuously observe the proportion of patients who are without progression at 16-weeks. Based on the hypothesized increase in median progression-free survival from the historical rate of 2 months to 3.33 months in either the ficlatuzumab arm or the ficlatuzumab plus cetuximab arm, the expected proportion

progression-free at 16 weeks would be 0.46 under the alternative hypothesis. A Bayesian predictive probability design was used to estimate the rejection regions to stop an arm for futility.⁵² The rejection regions to stop an arm for futility are: 0/8, 1/9, 2/13, 3/16, 4/19, 5/21, 6/24, 7/26, 8/28, 9/29, 10/31, 11/32, 12/33. Thus, if none of the first 8 patients is progression-free at 16 weeks, that arm will be stopped, or if only 1 of the first 9 patients is progression-free, that arm will be stopped, etc. This design has 80% power at $\alpha = 0.10$ with an expected sample size of 21.3 under the null hypothesis and 31.4 under the alternative hypothesis. The probability of early termination under the null hypothesis is 0.86. The rejection regions were derived to maximize power under the alternative hypothesis. There was no Bayesian predictive probability design with 90% statistical power given the proposed median survival times and sample size with $\alpha = 0.10$.

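### The 90% power in Section 10.3 ignores the mandatory futility rule in 10.7; with the rule enforced, power per arm is about 80% (at most about 0.88), and the success criterion is not named

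*Combined protocol and SAP*

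**What the plan says.** Section 10.3 sets the target for each arm as "improve the median PFS from 2 months to 3.33 months (i.e. 60% improvement in median PFS". It plans "66 eligible patients (33 eligible patients on each arm) over 24 months with an additional follow-up of 6 months" and states the operating characteristics as "using a log-rank test with 90% power while assuming a 0.10 one-sided type 1 error rate". Stopping is not mentioned. The same section ends with an advancement rule: "If one arm achieves the hypothesized median PFS, that arm will be advanced to phase III testing".

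Section 10.7 adds continuous futility monitoring of the 16-week progression-free proportion in each arm, from the eighth evaluable patient, with 13 boundaries running from 0/8 to 12/33. The wording is mandatory: "if none of the first 8 patients is progression-free at 16 weeks, that arm will be stopped", and so on along the list. The section gives the rule 80% power at alpha 0.10 and adds: "There was no Bayesian predictive probability design with 90% statistical power given the proposed median survival times and sample size" at that alpha.

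Section 10.6 describes the PFS analysis by arm in one sentence: "Progression-free and overall survival will be estimated for each arm using a Kaplan-Meier curve". It names no test against the historical 2 months.

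**The concern.** Two power figures, 90% and 80%, are given for the same arms, the same medians and the same sample size. Neither section says which applies to the trial. The 90% is a fixed-sample figure. Once an arm must stop on crossing a boundary, some arms that would have passed the log-rank test never reach it. Someone who takes the power from the sample-size section will believe that an active regimen has a 10% chance of being missed.

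The second difficulty is the decision itself. The section that powers a log-rank test advances an arm on a different condition, the monitoring section ends in what amounts to a binary test (at least 13 of 33 progression-free at 16 weeks), and the analysis section lists only estimation. Power and false-advance rate belong to a decision rule. Until the rule is named, neither can be read from the plan.

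**Working it through.** **Inputs.** From 10.3: historical median 2 months, target 3.33 months, 33 patients per arm, one-sided alpha 0.10 (z = 1.2816), 24 months of accrual plus 6 of follow-up. From 10.7: the 13 boundaries and a 16-week rate of 0.46 under the alternative. Assumed here: exponential PFS, uniform accrual, a one-sample log-rank test of each arm against the fixed 2-month median, and 16 weeks = 112/30.44 = 3.68 months. The 16-week rates are then 2^(−3.68/2) = 0.279 and 2^(−3.68/3.33) = 0.465.

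**Step 1: reproduce 10.3.** The one-sample log-rank approximation is power = Φ{[(1 − h)√E − z]/√h}, where h is the hazard ratio and E the number of events expected under the null. With h = 2/3.33 = 0.6006 and E = 33: (0.3994 × 5.745 − 1.2816)/0.775 = 1.307, so power is 0.904.

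An alternative is the one-sample exponential formula, events = [(z_α·λ0 + z_β·λ1)/(λ0 − λ1)]². At a ratio of 1.60 it gives (1.2816 × 2.60/0.60)² = 30.8 events, and 30.8/0.948 = 32.5, rounded up to 33 patients. At a ratio of 1.665 it needs only 28 patients. Simulated power at 33 patients and 3.33 months is 0.93 (0.94 with other variance forms).

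The 90% is therefore sound, or slightly conservative, as a per-arm calculation **without stopping**. Comparing the two arms with each other does not fit: 66 events would give only 0.785.

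**Step 2: reproduce 10.7.** Exact binomial recursion over the boundaries gives:

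| | 16-week rate 0.28 | 16-week rate 0.46 |
|---|---|---|
| Passes all boundaries | 0.099 | 0.804 |
| Expected sample size | 21.3 | 31.4 |
| Stopped by patient 32 | 0.856 | 0.154 |

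These match the plan's alpha of 0.10, power of 80%, sample sizes of 21.3 and 31.4, and early termination of 0.86. At 0.46, an arm with the hypothesised effect is stopped with probability 0.154 by patient 32, so no final test can then have power above 1 − 0.154 = 0.846. Adding 12/33 lowers that ceiling to 0.804.

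**Step 3: combine them.** Simulation of 200,000 arms per setting, one-sample log-rank z = (E − D)/√E > 1.2816 (D = observed events), with boundaries applied in order of accrual:

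| Decision rule | Advance, true median 3.33 | Advance, true median 2 |
|---|---|---|
| Log-rank, no stopping | 0.93 | 0.08 |
| Log-rank, counting only looks known before the 33rd enrolment | 0.87–0.88 | 0.07–0.08 |
| Log-rank, boundaries through 11/32 | 0.84 | 0.055 |
| Log-rank, all 13 boundaries | 0.80–0.81 | 0.05 |
| Boundaries alone (at least 13/33) | 0.80 at the plan's 0.46 | 0.10 |
| Observed median at least 3.33 months, with or without boundaries | 0.50 | 0.013 |

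With all boundaries enforced, about 0.126 of active arms would have had a significant log-rank result but are stopped (0.931 − 0.805 = 0.126).

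**Step 4: sensitivity.** A different variance in the log-rank statistic moves the second row to 0.88–0.89. Taking 16 weeks as 4.0 months lowers the three log-rank-with-stopping rows to 0.84–0.85, 0.76 and 0.71. At a true median of 3.2 months, power with all boundaries is about 0.76.

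**Step 5: the percentage.** 3.33/2 = 1.665, an improvement of 66.5%. A 60% improvement on 2 months is 3.2 months. The hazard ratio 2/3.33 is 0.60, which may be where the 60% came from.

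**The case against.** The strongest reply is that nothing is hidden. Section 10.7 states 80% power and says that 90% could not be reached with these medians and this sample size. Both figures reproduce, and what is missing is a cross-reference. That is fair on disclosure. It does not settle the matter, because 10.3 still states the 90% without qualification. Moreover, the 80% in 10.7 is the power of the 16-week count used as a test, not of the log-rank test after the looks. The two are both close to 0.80, but the plan never gives the second.

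Another reply is that 80% is the strictest reading. The plan does not say that an arm must both pass the log-rank test and reach 13/33, and at patient 33 no accrual is left to stop. This stands in part, and it is why the range up to 0.88 is given. Every reading with stopping remains below the same test's 0.93 without it.

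A third reply is that 60% may be the intended effect, since a ratio of 1.60 reproduces 33 patients under one formula. However, the log-rank approximation at a hazard ratio of 0.60 also gives 90% with 33. Further, 10.7's 0.46 agrees with 3.33 months (0.465) better than with 3.2 months (2^(−3.68/3.2) = 0.451). The percentage is the likelier slip, and the authors can confirm it.

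Finally, the design is non-comparative and its aim is described as estimation, so Kaplan-Meier curves suit that aim. Section 10.3 nevertheless states a test, an error rate, a power and a phase III advancement rule, and these need to agree.

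**Conclusion.** The concern holds. The 90% in 10.3 is the power of a fixed-sample log-rank test and is not delivered once the mandatory rule in 10.7 operates. At a true median of 3.33 months the procedure has power of about 0.80 with all boundaries enforced, 0.84 if 12/33 is not a stop, and about 0.88 on the most lenient reading. The risk of missing an active arm is thus 12–20%, against the 10% implied. Futility stopping lowers the false-advance rate (about 0.05 with all boundaries, against 0.08 for the simulated log-rank test alone), so the error lies in the stated power only.

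The unnamed success criterion matters more for the decision. Across the possible rules, the chance of advancing an arm with the hypothesised median runs from 0.50 to 0.93, and the chance of advancing an arm no better than the historical 2 months runs from 0.013 to 0.10. These figures are per arm and rest on exponential PFS, uniform 24-month accrual and 16 weeks = 3.68 months. The ceilings of 0.846 and 0.804 need only the plan's own 0.46 and its boundaries.

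**What to change.** - In 10.3, label the 90% as the power of the log-rank test without futility stopping. Add the power of the whole procedure, about 80% at 3.33 months with all boundaries enforced, with a cross-reference to 10.7.
- State in one sentence what decides success at full enrolment: the log-rank test, at least 13/33 progression-free at 16 weeks, both, or an observed median of at least 3.33 months. Say whether 12/33 is a stop, and make 10.6 list the chosen analysis.
- Give the false-advance rate for that rule. It is about 5% only if the log-rank test and all boundaries must both be passed.
- Correct the 60% improvement to about 67% (hazard ratio 0.60), after confirming that 3.33 months was the design input.

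The cost is wording: no extra patients and no change to the boundaries, but a less favourable stated power. This version is dated May 2023, after the March 31, 2021 limit on ficlatuzumab dosing. If results by arm are already known, the report should say that the criterion was clarified afterwards and show the outcome under each candidate rule.
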